#### 5.8.4. Toxicity Management of Infusion-Reactions Related to NC525

**Table 5** shows treatment guidelines for subjects who experience an infusion reaction associated with the administration of study drug. Signs and symptoms usually develop during or shortly after drug infusion and generally resolve completely within 24 hours of completion of infusion. Adverse events that may be manifestations of infusion reactions may include but are not limited to:

- Fever
- Chills/Rigors
- Flushing
- Nausea/Vomiting
- Bronchospasms
- Hypotension/Hypertension

To prevent infusion reactions from occurring all subjects must be premedicated prior to administration of NC525. Suggested premedication within 1.0 hour ( $\pm$  30 minutes) prior to infusion of NC525 is detailed below, however subjects may be premedicated based on institutional guidelines:

- Diphenhydramine 25 – 50 mg po or IV (or equivalent dose of antihistamine)
- Acetaminophen 500 – 1000 mg po or IV (or equivalent dose of analgesic)
- Ranitidine 150mg po (or equivalent dose of H2 antagonist)
- Solu-Cortef 100mg IV (or equivalent corticosteroid)

**Table 5: Infusion Reaction Dose Modification and Treatment Guidelines (NC525)**

NCI CTCAE v5.0 Grade of Sign or Symptom of Infusion-Related Reaction	Treatment	Premedication at Subsequent Dosing
Grade 1 Mild reaction	Increase monitoring of vital signs as medically indicated until the subject is deemed medically stable in the opinion of the investigator.	None
Grade 2  Requires therapy or infusion interruption but responds promptly to symptomatic treatment	Stop Infusion.  Additional appropriate medical therapy may include but is not limited to: 

• IV fluids

• Antihistamines

• Acetaminophen

• NSAIDs

• Narcotics

• Prophylactic medications indicated for <math>\leq 24</math> hrs

	Subject may be premedicated 1.5 h our ( $\pm$ 30 minutes) prior to infusion of study intervention with:  Diphenhydramine 50 mg po (or equivalent dose of antihistamine).  Acetaminophen 500-1000 mg po (or equivalent dose of analgesic).

NCI CTCAE v5.0 Grade of Sign or Symptom of Infusion-Related Reaction	Treatment	Premarketation at Subsequent Dosing
	
Increase monitoring of vital signs as medically indicated until the subject is deemed medically stable in the opinion of the investigator.
 
If symptoms resolve within 1 hour of stopping drug infusion, the infusion may be restarted at 50% of the original infusion rate (e.g., from 100 mL/hr. to 50 mL/hr.). Otherwise, dosing will be held until symptoms resolve and the subject should be premedicated for the next scheduled dose.
 
Discontinue study treatment permanently for subjects who develop a Grade 2 or higher hypersensitivity reaction despite adequate premedication.
	

Grades 3 or 4
 
Grade 3: Prolonged (i.e., not rapidly responsive to symptomatic medication and/or brief interruption of infusion); recurrence of symptoms following initial improvement; hospitalization indicated for other clinical sequelae (e.g., renal impairment, pulmonary infiltrates)
 
Grade 4: Life-threatening
	
Stop Infusion.
 
Additional appropriate medical therapy may include but is not limited to:
 
 
• IV fluids
 
• Antihistamines
 
• Acetaminophen
 
• Oxygen
 
• Corticosteroids
 
• Epinephrine**
 
• NSAIDs
 
• Narcotics
 
• Pressors
 
• Ventilator
 
 
Increase monitoring of vital signs as medically indicated until the subject is deemed medically stable in the opinion of the investigator.
 
Hospitalization may be indicated.
 
**In cases of anaphylaxis, epinephrine should be used immediately.
 
Subject is permanently discontinued from further study drug treatment.
	
No subsequent dosing

Abbreviations: IV = intravenous; NSAID = nonsteroidal anti-inflammatory drugs; po = orally.

Appropriate resuscitation equipment should be available at the bedside and a physician readily available during the period of drug administration. For further information, please refer to the Common Terminology Criteria for Adverse Events v5.0 (CTCAE) at <http://ctep.cancer.gov>.

The above table is the recommended guidance, however subjects should be managed per institutional guidelines.

## **5.9. Dose Limiting Toxicities (DLTs)**

### **5.9.1. Dose-Limiting Toxicity and Determination of Maximum Tolerated Dose**

During Dose Escalation, the evaluation period for DLTs will begin on Cycle 1 Day 1 and will continue up to 56 days. All DLTs will be assessed by the investigator using National Cancer Institute Common Terminology Criteria for Adverse Events (NCI CTCAE) v5.0. A DLT will be defined as the occurrence of any toxicity in [Table 6](#), except for events clearly associated with the underlying disease or an extraneous cause (e.g., car accident).

Individual subject dose reductions may be made based on events observed at any time during treatment with NC525; however, for the purposes of dose cohort escalation/de-escalation, and expanding a dose cohort, the decisions will be made based on events that are observed from the first day of study treatment through and including the 56-day DLT period. Alternative dose levels may subsequently be determined based on relevant toxicities that become evident after the 56-day DLT period.

**Table 6: Definition of Dose-Limiting Toxicity National Cancer Institute Common Terminology Criteria for Adverse Events (NCI CTCAE) v5.0**

Nonhematologic toxicity

Any grade 3 nausea, vomiting or diarrhea that requires TPN, tube feeding, or hospitalization is a DLT without exception

Any other grade 3 adverse reaction (including laboratory abnormalities) lasting more than 72 hours, with the following exceptions:

Grade 3 fatigue lasting >3 days

Any grade 4 nonhematological adverse reactions.

Any Hy's law case defined as:

Combined elevations in serum ALT >3 times the upper limit of normal (ULN) and bilirubin >2 ULN in the absence of alkaline phosphatase (ALP) elevation (<2 ULN). Note: Abnormal liver function tests as indicated by the criteria above will be considered a DLT if no other reason can be found to explain the combination of increased liver markers such as viral hepatitis A, B, or C; preexisting or acute liver disease; or another drug capable of causing the observed injury

Hematologic toxicity


Any grade >3 ANC or PLTS lasting more than 7 days is a DLT in the absence of active leukemia. Note: Patients with active leukemia are not evaluable for a hematological DLT.

General

Any infusion reaction that is not resolved within 24 hours.

Any adverse reaction that resulted in dose reduction or withdrawal.

Any fatal adverse reactions.

### **5.9.2. Management of Dose-Limiting Toxicities or Other Urgent Situations**

In all cases, investigators may employ any measures or concomitant medications, after discussion with the medical monitor (whenever possible), necessary to optimally treat the subject.

### **5.9.3. Follow-Up of Dose-Limiting Toxicities**

Any DLT should be followed until it resolves to baseline or appears to have stabilized for a minimum of 4 weeks (e.g., 28 days). During follow-up, subjects should be seen as often as medically indicated to assure safety.

## **5.10. Withdrawal/Discontinuation of Subjects from Study Treatment**

### **5.10.1. Withdrawal/Discontinuation Criteria**

Subjects may withdraw consent at any time for any reason or be removed from the trial at the discretion of the investigator should any untoward effect occur. In addition, a subject may be withdrawn by the investigator or the Sponsor if enrollment into the trial is inappropriate, the trial plan is violated, or for administrative and/or other safety reasons.

Discontinuation of study treatment does not represent withdrawal from the study. A subject may discontinue from treatment but agree to remain on-study, as long as the subject does not withdraw consent.

If a subject is withdrawn, then every reasonable effort should be made to determine the reason for withdrawal, and this information should be recorded in the electronic case report form (eCRF).

Subjects must be withdrawn from the trial for any of the following reasons:

- The subject is lost to follow-up
- Consent is withdrawn for study (does not agree to follow-up); no additional data collection should occur

Subjects must discontinue from the study treatment but can continue to be monitored for any of the following reasons:

- Consent is withdrawn for treatment (agrees to follow-up)
- The subject becomes pregnant
- Confirmed progressive disease (except if Sponsor approves treatment continuation)
- Unacceptable adverse experiences
- Investigator's decision to withdraw subject
- Subjects proceed to stem cell transplantation
- Discontinuation of treatment may be considered for subjects who have attained a confirmed CR, CRh, or CRi and have been treated for two years with NC525
- Any study intervention-related toxicity specified as a reason for permanent discontinuation as defined in the guidelines for dose modification due to AEs in [Section 5.8](#).
- The study is terminated by the IRB, regulatory authority, or Sponsor

Subjects who discontinue study treatment but agree to remain on-study should continue to be followed according to the applicable Post-Treatment Follow-up schedule. All subjects will be followed for overall survival (OS) until death, withdrawal of consent, or the end of the study.

### **5.10.2. Withdrawal Procedures**

If the decision is made to permanently discontinue the study treatment, an end-of-treatment (EOT) visit should be conducted. The date on which the decision was made to discontinue study treatment and the reason for treatment discontinuation will be recorded in the eCRF.

If a subject discontinues study treatment, the site monitor and Sponsor must be notified.

## **5.11. Concomitant Therapy During Study Treatment**

All treatments that the investigator considers necessary for a subject's welfare may be administered at the discretion of the investigator in keeping with the community standards of medical care.

Certain medications or vaccinations are specifically prohibited prior to and during the study. If there is a clinical indication for one of these medications or vaccinations specifically prohibited during the study, discontinuation from study drug or vaccination may be required. The investigator should discuss any questions regarding this with the medical monitor. The final decision on any supportive therapy or vaccination rests with the investigator and/or the subject's primary physician. However, the decision to continue the subject on study drug or vaccination schedule requires the agreement of the investigator, the sponsor, and the subject.

### **5.11.1. Prohibited Concomitant Medications**

**Subjects are prohibited from receiving the following therapies during the treatment period of this study:**

- Antileukemic systemic chemotherapy or biological therapy
- Investigational agents other than NC525
- Live or live attenuated vaccines
- Hematopoietic growth factors (G-CSF, GM-CSF, ESA)
- Steroid therapy during study participation should be limited to a lower dose and short duration if medically indicated. Exceptions can be inhalational steroids for the treatment of asthma or COPD, topical steroids and for prevention and/or treatment of transfusion-related reactions.
- Receipt of calcineurin inhibitors (CNI) while participating in the study

If the investigator determines that a subject requires any of the aforementioned treatments for any reason, all study treatments of NC525 must be discontinued.

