#### **3.4.2. Replacement of Subjects**

Subjects may be replaced for any of the following reasons:

- If a subject withdraws from treatment before the completion of the DLT period for any reason other than a DLT (e.g., subject is not evaluable for DLTs)
- Subject does not meet the eligibility requirements of the study (accidental enrollment)

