**Table 4: Dose Modifications for Adverse Events**

AE Toxicity grade (CTCAE V5.0)	Action with NC525
Grade 3 Immune-related AE (e.g. pneumonitis, colitis, elevated LFTs (in absence of active disease), etc.)	Interrupt Treatment, Restart treatment at one dose level lower when the specific immune-related AE resolves to no more than Grade 1 in severity. If immune-related AE does not resolve in 14 days, or if the Grade 3 immune-related AE recurs, the subject must permanently discontinue.
Grade 4 Immune-related AE (e.g. pneumonitis, colitis, elevated LFTs (in absence of active disease), etc.)	Permanently Discontinue

AE Toxicity grade (CTCAE V5.0)	Action with NC525
Grade 3 or Grade 4 Tumor Lysis Syndrome (TLS)	
Interrupt Treatment, Restart treatment at the same dose when the TLS is resolved to no more than Grade 1 in severity within 2 weeks or 14 days,
 
For Management of TLS, see Appendix 5

Any Grade Infusion Reaction	See Table 5 for management of infusion reaction.
(Grading based on reporting of individual symptoms)	
Interrupt Treatment, Administer corticosteroids per standard of care. Restart treatment at the same dose level with the DS is resolved within 2 weeks or 14 days.

New Onset Grade 4 Neutrophil Count Decrease lasting > 1 week b	
Interrupt Treatment, Restart treatment at the same dose when the ANC is <math>\geq 500/\mu\text{L}</math> within 2 weeks or 14 days.
 
If Grade 4 neutropenia recurs, interrupt again but restart at one dose level lower when the ANC is <math>\geq 500/\mu\text{L}</math> within 2 weeks or 14 days.

New Onset Grade 4 Platelet Count Decrease lasting > 1 week b	
Interrupt Treatment, Restart treatment at the same dose when the platelet count <math>\geq 25,000/\mu\text{L}</math> within 2 weeks or 14 days.
 
If Grade 4 thrombocytopenia recurs, interrupt again but restart at one dose level lower when the platelet count is <math>\geq 25,000/\mu\text{L}</math> within 2 weeks or 14 days.

Any other non-hematological Grade 3 (other than TLS) adverse reaction	
Interrupt Treatment, Restart treatment at the same dose if the adverse reaction resolved to no more than Grade 1 in severity within 2 weeks or 14 days.
 
If the adverse reaction recurs at Grade 4, the subject must permanently discontinue.
 
If the adverse reaction recurs a second time at Grade 3, interrupt again, and the subject must permanently discontinue.

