Any other non-hematological Grade 4 (other than TLS) adverse reaction	Permanently Discontinue

a Differentiation Syndrome as determined per PI based on institutional guidelines and in the absence of active infection, infusion reaction, heart failure, etc., with any of the following potential signs and symptoms: unexplained fever, weight gain, peripheral edema, dyspnea with interstitial pulmonary infiltrates, pleural and/or pericardial effusion, hypotension, acute renal failure, with or without increasing total WBC.

b In the absence of active myeloid neoplasms.

**Note:** For subjects who have not recovered ANC  $\geq$  500/ $\mu$ L or platelet count  $\geq$  25,000/ $\mu$ L within 14 days of drug interruption, a repeat bone marrow biopsy and aspirate may be performed to rule out active myeloid neoplasms at the investigator discretion before resuming the next cycle of study treatment.

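### The closing sentence of 5.11.1, read literally, stops NC525 whenever steroids are needed, which contradicts Table 4's treat-and-restart rule for differentiation syndrome

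*Combined protocol and SAP*

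**What the plan says.** Section 5.11.1 (Prohibited Concomitant Medications) includes a steroid bullet: "Steroid therapy during study participation should be limited to a lower dose and short duration if medically indicated." It names inhaled, topical and transfusion-reaction use as possible exceptions. It names neither DS nor NC525 premedication. The section then closes: "If the investigator determines that a subject requires any of the aforementioned treatments for any reason, all study treatments of NC525 must be discontinued."

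Table 4 (Section 5.8.2) handles DS differently. After interruption of NC525 it says: "Administer corticosteroids per standard of care. Restart treatment at the same dose level with the DS is resolved within 2 weeks or 14 days." Footnote a leaves the diagnosis to the site: "Differentiation Syndrome as determined per PI based on institutional guidelines."

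Section 5.8.4 states that "all subjects must be premedicated prior to administration of NC525". Its suggested regimen includes 100 mg of intravenous hydrocortisone or an equivalent, and institutional guidelines may be used instead.

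For DLT scoring, the general rows of Table 6 (Section 5.9.1) count: "Any adverse reaction that resulted in dose reduction or withdrawal."

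**The concern.** The two instructions cannot both be followed for a subject with DS who needs a standard-of-care steroid course. One resumes NC525; the other ends it. DS is a foreseeable event here. Section 9.1.3 makes it an event of clinical interest, Table 4 gives it a management row, and Section 10.2.2 gives it its own provision in the expansion stopping rule.

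The stake is the DLT count in dose escalation, on which the MTD rests. With cohorts of three, that count should not depend on which section a site follows. A subject whose DS has resolved could also lose treatment that Table 4 would have resumed.

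**Working it through.** **1. The provisions side by side, for DS treated with corticosteroids.**

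- Table 4: interrupt, treat, restart at the same dose if resolved within 14 days.
- 5.11.1, steroid bullet: steroids are tolerated if low in dose and short. Neither limit is given a number, and Table 4 sets no cap on the DS course.
- 5.11.1, closing sentence: any listed treatment, whatever the reason, ends NC525.
- 5.11 (parent section): discontinuation is only a possibility, and a subject may continue if investigator, sponsor and subject agree.
- 5.10.1: toxicity-driven stops follow Section 5.8. Need for a prohibited medication is not on its list of reasons to stop.
- 5.9.2: any necessary medication may be given after discussion with the medical monitor. It does not say whether NC525 then continues.

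Most of this favours Table 4. The closing sentence of 5.11.1 is the outlier, but it is the one in mandatory form.

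**2. Which DS is affected.** Table 6 counts most Grade 3 reactions only if they last more than 72 hours, and counts all Grade 4 non-hematologic and all fatal reactions. DS of Grade 1–2, or Grade 3 resolving within 72 hours, therefore generally meets no grade-based row. Only the dose-reduction-or-withdrawal row could make it a DLT.

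**3. Scoring that subject.**

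- Table 4 followed: held, restarted at the same dose, completes 56 days. Evaluable, no DLT.
- 5.11.1 followed literally: stopped because a reaction required steroids. Evaluable, because Section 3.2.1 counts a subject who stops early for an adverse event, and most naturally a DLT by withdrawal.

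**4. Effect on Table 1.** The boundaries reproduce first. With target φ = 0.25 (Section 10.2.1) and interval limits of 0.6φ and 1.4φ (an assumption; the protocol does not state them), the BOIN cut-offs are 0.197 for escalation and 0.298 for de-escalation. For n = 6, 1/6 = 0.167 gives escalate and 2/6 = 0.333 gives de-escalate, as in Table 1. For n = 3, 0/3 gives escalate. Plain BOIN would de-escalate at 1/3 = 0.333; Table 1 says stay, consistent with the nested 3+3 rule in Section 3.1.

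Adding one DLT for the affected subject:

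| Other DLTs | Under Table 4 | Under literal 5.11.1 |
|---|---|---|
| 0 among 3 subjects | 0/3, escalate | 1/3, stay |
| 1 among 6 subjects | 1/6, escalate | 2/6, de-escalate |

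**5. Illustration only.** The documents give no DS rate. Assume a rate b = 0.10 of other DLTs and, independently, a rate d of such DS, with every such subject scored as a DLT. Then p = 1 − (1 − b)(1 − d), and the chance of escalating by n = 6 is (1 − p)³ + 3p(1 − p)² × (1 − p)³.

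- d = 0 (equivalent to Table 4): p = 0.10; 0.729 + 0.177 = 0.906
- d = 0.05: p = 0.145; 0.625 + 0.199 = 0.824
- d = 0.10: p = 0.190; 0.531 + 0.199 = 0.730
- d = 0.20: p = 0.280; 0.373 + 0.163 = 0.536

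These show direction under assumed rates and uniform literal application. They do not estimate what will happen in this trial.

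**The case against.** The best defence is that 5.11.1 should not be read literally. Its steroid bullet is a limit, not a ban, and a literal closing sentence would cancel the bullet's own permissions. Table 4 is the specific instruction and 5.11.1 the general one. Sections 5.11 and 5.10.1 point the same way. DS reaches the sponsor within 24 hours as an event of clinical interest, the Clinical Study Team reviews cohort data jointly, and Table 1 informs its decision without binding it. Most sites would probably follow Table 4.

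Much of this stands and limits the point. It does not remove the conflict: a standard-of-care DS course may not count as low dose, and the closing sentence admits no reason as an exception. The team's adjudication role in Section 9.5 is worded for high-grade events, so it does not expressly reach Grade 1–2 DS.

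Two stronger readings are tempting and are not supported:

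- A reader might infer that every premedicated subject must stop NC525. That cannot be intended. One premedication dose plausibly falls within the bullet's allowance, and the steroid is suggested, not required. What is missing is an explicit exemption.
- A reader might infer a third scoring, in which the subject is replaced without a DLT, because Section 3.4.2 allows replacement "If a subject withdraws from treatment before the completion of the DLT period for any reason other than a DLT". That is strained. It attributes the stop to the medication and ignores the adverse event that required it, whereas Section 3.2.1 treats a subject stopped early for an adverse event as evaluable.

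**Conclusion.** The inconsistency is real and should be corrected. It is a conflict of wording; no design figure changes. Its reach is DS in the 56-day window of dose escalation that meets no grade-based row of Table 6. Two scorings are at issue: no DLT under Table 4, or most naturally a DLT by withdrawal under a literal 5.11.1. A single subject is enough to change the Table 1 action at 3 or 6 evaluable subjects.

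How often this would happen cannot be estimated from the documents. A reader might also infer that the expansion monitoring is exposed. It largely is not: Section 10.2.2 excludes DS from the toxicity count unless it is Grade 3 or higher and unresolved within 7 days. The conclusion assumes only that some sites could apply the closing sentence of 5.11.1 as written.

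**What to change.** Extend the closing sentence of 5.11.1 with: *except steroid use within the limits and exceptions stated above, and corticosteroids given under Section 5.8 (premedication under 5.8.4, or adverse event management under Table 4 or Table 5), for which Section 5.8 determines whether NC525 continues.*

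The first half of the clause matters. Naming only DS and premedication would imply that the bullet's inhaled, topical, transfusion-related and short low-dose uses force discontinuation. A note in Table 6 that a DS hold with same-dose restart is not a withdrawal is optional, because Table 4 already separates interruption from permanent discontinuation.

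The cost is one clause and no new data. The text becomes slightly less conservative than a literal 5.11.1 for DS that resolves. All rows of Table 6 still apply, so Grade 3 reactions lasting beyond 72 hours, Grade 4 and fatal reactions, dose reductions and true withdrawals still count as before.

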## 6. SCHEDULE OF STUDY PROCEDURES

**Table 7: Schedule of Study Procedures**

### CYCLES 1 AND 2 (WEEKLY (QW) DOSING)

Trial Period	Protocol Section	Screening Phase	Treatment b (28- day cycles)											Disease Assessment	Post-Treatment		
			Cycles 1 & 2												Day 28 or at Suspected PD	End of Treatment (EOT)	30-Day Safety Follow-Up bb
Visit Day	Screening	Day -1 (Cycle 1 Only)	Day 1	Day 2	Day 3	Day 4	Day 8	Optional Day 14 (Cycle 1 Only)	Day 15	Day 16	Day 17	Day 18	Day 22				
Scheduling Window (Days)	~ 21 Days		+1 day (Cycle 2)				+1 day		+1 day				+1 day	± 3 days		± 2 weeks	Every 2 Months
ADMINISTRATIVE PROCEDURES																	
Informed consent a	0	X															
Eligibility (I/E) criteria	4	X															
Demographics	8.3.1	X															
Medical History e	8.3.1	X															
Cancer History and Diagnosis	8.3.2	X															
Prior/Concomitant Medications f	8.4	←	X											→			
Document PRBC and platelet transfusions	8.4	←	X											→			
Post-Treatment Cancer Therapy	8.5														X	X	X
Survival Status	7.5.2				←	X											

Trial Period	Protocol Section	Screening Phase	Treatment b (28- day cycles)											Disease Assessment	Post-Treatment			
			Cycles 1 & 2												Day 28 or at Suspected PD	End of Treatment (EOT)	30-Day Safety Follow-Up bb	Survival Follow-Up cc
Visit Day	Protocol Section	Screening	Day -1 (Cycle 1 Only)	Day 1	Day 2	Day 3	Day 4	Day 8	Optional Day 14 (Cycle 1 Only)	Day 15	Day 16	Day 17	Day 18	Day 22				
Scheduling Window (Days)		~ 21 Days		+1 day (Cycle 2)				+1 day		+1 day				+1 day	± 3 days		± 2 weeks	Every 2 Months
CLINICAL PROCEDURES																		
Administer NC525 c,s	5.2.2			X				X		X				X				
Comprehensive PE g	8.6.2.1	X														X		
Targeted PE h	8.6.2.2			X				X		X				X	X			
TLS Prophylaxis and Monitoring d	5.8.3		X	X	X	X		X		X	X	X		X				
Vital signs and weight i	8.6.4	X		X	X	X	X	X	X	X	X	X	X	X	X	X		
Height	8.6.4	X																
ECOG performance	8.6.3	X		X				X		X				X				
12-lead ECG j	8.6.77	X																
AE assessment k	9.1		◀	X											▶			
LOCAL LABORATORY																		
Hematology with differential	Table 8	X l		X m	X	X		X	X	X n	X	X	X	X	X	X		
Comprehensive CMP	Table 8	X l		X m	X	X		X	X	X n	X	X		X	X	X		
Coagulation panel	Table 8	X l		X m				X		X n				X				
Urinalysis o	Table 8	X l																
Inflammatory Markers	Table 8	X l		X				X		X								
Hepatitis B and C	Table 8	X l																

Trial Period	Protocol Section	Screening Phase	Treatment b (28- day cycles)											Disease Assessment	Post-Treatment			
			Cycles 1 & 2												Day 28 or at Suspected PD	End of Treatment (EOT)	30-Day Safety Follow-Up bb	Survival Follow-Up cc
Visit Day	Protocol Section	Screening	Day -1 (Cycle 1 Only)	Day 1	Day 2	Day 3	Day 4	Day 8	Optional Day 14 (Cycle 1 Only)	Day 15	Day 16	Day 17	Day 18	Day 22				
Scheduling Window (Days)		~ 21 Days		+1 day (Cycle 2)				+1 day		+1 day				+1 day	± 3 days		± 2 weeks	Every 2 Months
Pregnancy Test	Table 8	X q		X r				X r		X r				X r		X q		
Bone Marrow Aspirate and Biopsy Local Disease Assessment (Flow Cytometry, Cytogenetics, Morphology)	Table 10	X x							XY						X z	X dd		X ee
CENTRAL LABORATORY																		
Pharmacokinetics (PK) t	Table 9			X	X	X	X	X		X	X	X	X	X				
Anti-Drug Antibodies (ADA) u	Table 9			X						X						X		
Cytokines w	Table 9			X				X		X				X				
Bone Marrow Immunophenotyping v	Table 10	X							XY						X			
Bone Marrow Aspirate and Biopsy (Smear, Touch Prep, or FFPE) p	Table 10	X							XY						X			

